6.3. Lifestyle Restrictions

Participants will abstain from strenuous exercise for 24 hours before each blood collection for clinical laboratory test.

6.4. Screen Failures

Participants who do not meet all inclusion, exclusion and any other eligibility criteria will be considered Screen Failures. Basic study data will be collected for all screened participants including the reason for screen failure to meet the Consolidated Standards of Reporting Trials (CONSORT) publishing requirements and to respond to queries from regulatory authorities. Participants are allowed to rescreen once but the participant will be assigned a new participant number. Participants who are administered oral CAB (or oral phase) and subsequently withdrawn from the study, for any reason, may not be re-screened.

7. TREATMENTS

Study treatment is defined as any investigational treatment intended to be administered to a study participant according to the study protocol.

7.1. Treatments Administered

7.1.1. Study Treatments

Table 4 Study Treatments

Study Treatment		
Product Name:	Oral CAB	CAB-LA
Dosage Formulation	Tablet	Sterile Suspension for Injection Vial
Unit dose strength(s)/Dosage level(s):	30 mg tablet Dose level = 1 tablet	200 mg/mL sterile suspension Dose level = 600 mg (3 mL)
Route of Administration	Oral	Intramuscular injection
Dosing instructions	Administer orally, once daily. Dose at same time daily without regard to food with water	Intramuscular Injection. See instructions in Study Reference Manual (SRM) for preparation and administration
Packaging and Labeling	Study Treatment will be provided in high density polyethylene (HDPE) container. Each container will be labeled as required per country requirement.	Study Treatment will be provided in USP Type I glass vial with a 13 mm gray stopper and an orange colored plastic flip off overseal. Each vial will be labeled as required per country requirement.

USP United States Pharmacopeia

7.1.2. GSK1265744 – Tablet (CAB)

The investigational product (IP) CAB is manufactured by GlaxoSmithKline (GSK) and is formulated as white to almost white oval shaped film coated 30 mg tablets for oral administration, packaged in HDPE bottles with child-resistant closure that include an induction seal. The CAB tablets will be packaged in bottles containing 30 tablets each. Participants must keep all IP in its original package container. CAB tablets are to be stored up to 30°C and protected from moisture.

7.1.3. GSK1265744 – Injectable Suspension (CAB LA)

The IP CAB LA is manufactured by GSK and is a sterile white to slightly colored suspension containing 200 mg/mL of CAB as free acid for administration by IM injection. The product is packaged in a 3 mL USP Type I glass vial with a 13 mm gray stopper and an orange colored plastic flip off overseal. Each vial is for single use

containing a withdrawable fill of 2.0 mL, and does not require dilution prior to administration. CAB LA injectable suspension is to be stored at up to 30°C, do not freeze. Participants will be assigned to study treatment in accordance with the schedule mentioned in SoA (Table 1).

Vials of CAB LA are supplied as a suspension and need no further dilution or reconstitution. However, sites should gently invert the vials a few times to re-suspend sediments and allow bubbles to subside, and then use a syringe to withdraw the required volume of suspension for IM injection.

All injections must be given intramuscularly in the gluteus medius. Sites may use their discretion as to where in the gluteus muscle each injection is given according to individual participant circumstance. The time of injection will be captured in the electronic case report form (eCRF).

IM injections should be administered at a 90 degree angle into the gluteus medius muscle using a 1.5” – 2.5” 21-25 gauge needle (or sizes outside of this suggested range based on investigator judgement). The needle should be long enough to reach the muscle mass and ensure an IM injection, but not so long as to involve underlying nerves, blood vessels, or bone. Longer needle lengths will be required for participants with higher BMIs, to ensure that injections are administered intramuscularly as opposed to subcutaneously. BMI, needle gauge, and length will be collected in the eCRF.

For participants with a higher BMI the investigator should consider using a longer needle, see SRM for details.

In the event of suspected intravenous administration, a PK sample will also be drawn approximately 2 hours post dose for evaluation of CAB plasma concentrations. Detailed dosing instructions can be found in the SRM.

7.2. Dose Modification

Dose modification will not be permitted in this study. Data from this study may be the basis of future dose modifications for subsequent studies.

7.3. Method of Treatment Assignment

This will be an open label, non-randomized, single arm study. Participants will receive daily oral CAB (30 mg tablets) for 4 weeks during the Oral Phase of the study and IM injections of 600 mg of CAB LA at Week 5, Week 9, Week 17, Week 25 and Week 33 during the Injection phase. For details of dosing refer to Section 2.

7.4. Blinding

This will be an open label, non-randomized, single arm study.

7.5. Preparation/Handling/Storage/Accountability

- The investigator or designee must confirm appropriate temperature conditions have been maintained during transit for all study treatment received and any discrepancies are reported and resolved before use of the study treatment.
- Only participants enrolled in the study may receive study treatment and only authorized site staff may supply or administer study treatment. All study treatments must be stored in a secure, environmentally controlled, and monitored (manual or automated) area in accordance with the labeled storage conditions with access limited to the investigator and authorized site staff.
- The investigator, institution, or the head of the medical institution (where applicable) is responsible for study treatment accountability, reconciliation, and record maintenance (i.e., receipt, reconciliation, and final disposition records). Take adequate precautions to avoid direct eye or skin contact. In the case of unintentional occupational exposure notify the monitor, Medical Monitor and/or GSK study contact.
- Further guidance and information for the final disposition of unused study treatment are provided in the SRM.
- Under normal conditions of handling and administration, study treatment is not expected to pose significant safety risks to site staff.
- A Material Safety Data Sheet (MSDS)/equivalent document describing occupational hazards and recommended handling precautions either will be provided to the investigator, where this is required by local laws, or is available upon request from GSK.

7.6. Treatment Compliance

- When participants are dosed at the site, they will receive study treatment directly from the investigator or designee, under medical supervision. The date and time of each dose administered in the clinic will be recorded in the source documents. The dose of study treatment and study participant identification will be confirmed at the time of dosing by a member of the study site staff other than the person administering the study treatment.
- During the oral dosing phase, compliance will be assessed through querying the participant during the site visits and documented in the source documents and CRF. A record of the number of CAB tablets dispensed to and taken by each participant must be maintained and reconciled with study treatment and compliance records. Treatment start and stop dates, including dates for treatment delays and/or dose reductions will also be recorded in the CRF.
- CAB LA 600 mg at weeks 5, 9 and every 8 weeks up to 33 weeks will be intramuscularly administered to participants at the site. Administration will be documented in the source documents and reported in the CRF.

Note:

- CAB LA dosing is expected to occur in a window ± 3 Days

- CAB LA dosing may occur without consultation from the medical monitor if performed within this dosing window.

Any request for dosing to occur outside of the dose week must be discussed and agreed with the medical monitor prior to dosing. In the event of a late dose, a revised dosing schedule for subsequent dosing may be required and will be communicated to the site staff at the time of approval for continued dosing.

7.7. Concomitant Therapy

Any medication or vaccine (including over-the-counter or prescription medicines, vitamins, and/or herbal supplements including traditional Chinese medicines) that the participant is receiving at the time of enrolment or receives during the study must be recorded along with:

- reason for use
- dates of administration including start and end dates
- dosage information including dose and frequency

The Medical Monitor should be contacted if there are any questions regarding concomitant or prior therapy.

7.7.1. Permitted Medications and Non-Drug Therapies

Not applicable.

7.7.2. Prohibited Medications and Non-Drug Therapies

Experimental agents not otherwise specified in the protocol, cytotoxic chemotherapy, antiretroviral therapy, or radiation therapy may not be administered. Systemically administered immunomodulators are prohibited.

The following medications could significantly decrease the levels of CAB in the blood due to enzyme induction and therefore must not be administered concurrently:

- carbamazepine
- oxcarbazepine
- phenobarbital
- phenytoin
- rifabutin
- rifampin
- rifapentine
- St. John's wort

The following medications are anticoagulant/antiplatelet medications and could interfere with the ability to receive intramuscular injections. Their use is prohibited within 7 days before and for 7 days after the injection:

- high dose aspirin
- anagrelide
- apixaban
- argatroban
- bivalirudin
- clopidogrel
- dabigatran
- dalteparin
- enoxaparin
- fondaparinux
- heparin
- lepirudin
- prasugrel
- rivaroxaban
- ticagrelor
- ticlopidine
- warfarin

7.8. Treatment after the End of the Study

Participants will not receive any additional treatment after completion of the study.

8. DISCONTINUATION CRITERIA

8.1. Discontinuation of Study Treatment

Participants who discontinue study treatment during the oral phase will be withdrawn from the study. Participants who discontinue treatment during the injection phase should be followed up for at least 56 weeks after their last injection as per the schedule of activities.

[figure not shown]
8.1.1. Liver Chemistry Stopping Criteria

Liver chemistry stopping and increased monitoring criteria have been designed to assure participant safety and evaluate liver event etiology (in alignment with the FDA premarketing clinical liver safety guidance). These protocol guidelines are in alignment with FDA premarketing clinical liver safety guidance:
<http://www.fda.gov/downloads/Drugs/GuidanceComplianceRegulatoryInformation/Guidances/UCM174090.pdf>.

Discontinuation of study treatment for abnormal liver tests is required when

- a participant meets one of the conditions outlined in the algorithm
- or
- when in the presence of abnormal liver chemistries not meeting protocol-specified stopping rules, the investigator believes study treatment discontinuation is in the

best interest of the participant **Phase I Liver Chemistry Stopping Criteria – Liver Stopping Event Algorithm**

Liver Safety Required Actions and Follow up Assessments Section can be found in [Appendix 6](#).

8.1.2. Temporary Discontinuation

Temporary discontinuation is not allowed.

8.1.3. Follow up visits for participants withdrawn from IM dosing

Participants that are withdrawn from study treatment will continue to be followed for 56 Weeks. All participants who have received at least 1 injection will be followed as per the follow-up phase of the study. Starting eight weeks post last injection, participants will be seen once every 12 weeks for up to 48 weeks.

At each visit the following long term follow up procedures will be performed:

- HIV POC test
- HIV counselling
- Offer condoms and lubricant
- Adverse event and SAE review
- Concomitant medication review
- Liver function tests
- Plasma sample for drug level
- Plasma sample for storage

Final visit will be performed at 56 weeks post last injection (see Section 2) Week 89.

8.1.4. Rechallenge

8.1.4.1. Study Treatment Restart or Rechallenge

Study treatment restart or rechallenge after the stopping criteria are met by any participant participating in this study is not allowed.

8.2. Withdrawal from the Study

8.2.1. Withdrawal from the Study Treatment

A participant may withdraw from the study treatment at any time at his/her own request, or may be withdrawn at any time at the discretion of the Investigator for safety, behavioral or administrative reasons. Participants that are discontinued from treatment during the Oral Phase will end their participation at that time. Participants that are discontinued from treatment during the Injection phase will enter the post treatment period unless consent is withdrawn. All participants who have received at least 1 injection of CAB LA will be followed as per the follow-up phase of the study. Starting eight weeks post last injection, participants will be seen once every 12 weeks for up to 48 weeks. Every effort should be made to complete the early termination study procedures and observations if the participant does not enter post-treatment follow-up.

Any laboratory parameter that meets the stopping criteria should be repeated once to confirm the value prior to withdrawal

Reasons for study treatment discontinuation during the Oral or Injection Phase may include:

- Confirmed HIV acquisition
- Any clinically significant AE deemed to require discontinuation of investigational product
- Grade 3 or higher rash or Grade 2 rash with evidence of systemic involvement
- Grade 2 or higher allergic reaction
- Post entry co-enrolment in an HIV prevention study
- Use of PrEP during the course of the study
- Behaviors assessed by the investigator as being at “high risk” for HIV infection during the course of the study

These thresholds assume that participants are asymptomatic with respect to these changes. In the presence of clinically significant symptoms, lower thresholds for these parameters may need to be used for consideration of possible withdrawal of participants from the study treatment, after consultation between the Principal Investigator and a Medical Monitor.

Before discontinuing a participant from investigational product(s), the Investigator must contact the Medical Monitor. In the event that the investigator is unable to reach the

Medical Monitor, the Investigator, at his or her discretion, may withhold investigational product(s) from a participant until the Medical Monitor or designee can be contacted.

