- HIV PoC (Point of care) test will be performed at each time point during the course of the study and must be reviewed prior to IM dosing. See [Appendix 9](#) for the HIV testing algorithm at screening, Day 1 and during the course of the study.
- ECGs will be performed following 5 minutes of rest in a semi-supine position.
- Liver Chemistry Tests include Alanine aminotransferase (ALT), Aspartate aminotransferase (AST), Bilirubin total and direct.

- m. Oral Pharmacokinetic (PK) sampling at trough will be collected for all subjects prior to dose within 20 to 28 hours following oral administration the day prior. Intensive oral PK sampling will be collected from approximately 16 participants as shown in [Table 2](#).
- n. PK sampling for Injection phase: All PK samples will be collected prior to CAB LA injections at Week 5, 9, 17, 25, and 33 with the exception of 1-week post injection samples at Weeks 6, 10, 18, 26, 34, week 37(4-week post injection sample) and Week 41
- o. Long-term follow up PK samples: PK sampling during follow up will occur at, Week 53, 65, 77, and 89.
- p. Additional testing is required for participants who have a reactive or positive HIV test after enrolment. Stored plasma from the visit previous to the positive test should be tested for HIV using the 4th generation HIV test to best estimate time of infection. HIV acquisition must be confirmed by either western blot, HIV ½ Multispot or the Geenius HIV Confirmation ½ Assay, and HIV RNA.
- q. Visit may occur in a window ± 3 Days

Table 2 SCHEDULE OF INTENSIVE ORAL PK APPROXIMATELY 16 PARTICIPANTS) ^{a,b}

	Day 25	Day 26	Day 27							Day 28	
	Check-in	Oral dose administered (e.g. 8AM)	Prior to oral dose (e.g. 7:55AM)	Oral dose administered (e.g. 8AM)	1-hour post dose (e.g. 9AM)	2-hour post dose (e.g. 10AM)	3-hour post dose (e.g. 11AM)	4-hour post dose (e.g. 12AM)	8-hour post dose (e.g. 4PM)	24-hour post dose (e.g. 8AM)	Oral dose administered (e.g. after 8 AM)
Plasma for CAB concentration			X		X	X	X	X	X	X	

- a. PK sampling may occur ± 15 min
- b. Central lab tests for the intensive oral PK subjects refer to [Table 1](#).

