8.2.2. Withdrawal of Informed Consent

- If the participant withdraws consent for disclosure of future information, the sponsor may retain and continue to use any data collected before such a withdrawal of consent.
- If a participant withdraws from the study, he/she may request destruction of any samples taken and not tested, and the investigator must document this in the site study records.
- Refer to the SoA for data to be collected at the time of study discontinuation and follow-up and for any further evaluations that need to be completed.

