10.3.2. Secondary Analyses

Acceptability

To assess acceptability of the CAB LA, the proportion (with 95% CI) of participants who would consider using CAB LA for HIV prevention in the future will be calculated among all enrolled participants (including those who terminated product use during the trial). Participants will be asked if they would consider using CAB LA for HIV prevention in the future at their Week 41 visit or at their withdrawal visit, whichever occurs first.

Tolerability

To assess tolerability of CAB LA, the proportion of participants who terminate from receiving injections prior to the full course due to AE, intolerability of injection, frequency of injections, or burden of procedures related to injections out of those participants that received at least one injection.

A questionnaire will also be used to assess participant tolerability and satisfaction to the treatment. For each question the responses will be summarized by the proportion of participants reporting the response out of all those that answered the question. An overall treatment satisfaction score will be calculated for each participant.

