8.2. Safety and Tolerability Analyses of Oral CAB

The safety and tolerability analyses of oral CAB will include Grade 2 or higher clinical and laboratory events occurred during the oral phase. Analysis time frame is from the first date of taking oral CAB tablet to the date right before the first CAB LA injection. For subjects who withdraw treatment from the oral phase, the analysis will include all safety and tolerability assessments from the first date of taking oral CAB tablet up to the date of last study visit.

Safety endpoints including adverse events, laboratory test, vital signs, and death will be analysed. The same analysis approaches will be conducted as in the primary analysis, but with different time frame.

[Table 13](#) provides an overview of the planned analyses, with full details of data displays being presented in [Appendix 14](#): List of Data Displays.

Table 13 Overview of Planned AE, LB, VS, and Death Analyses

Display Type	Data Displays Generated						
	Stats Analysis			Summary		Individual	
	T	F	L	T	F	F	L
AE Analyses							
All AEs				Y			Y
Grade 2 or higher AEs				Y			Y
SAEs				Y			Y
AE leading to treatment discontinuation or study withdrawal				Y			Y
Drug-related AEs				Y			
Drug-related SAEs				Y			
Drug-related Grade 2 or higher AEs				Y			
Common AEs				Y			
Common non-serious AEs				Y			
Common Grade 2-4 AEs				Y			
Common drug-related Grade 2-4 AEs				Y			
Laboratory Tests							
Grade 2 or higher laboratory events				Y			
Clinical Chemistry				Y			Y
Hematology				Y			Y
Fasting Lipid Profile				Y			Y
Urinalysis				Y			Y
Coagulation Profile				Y			Y
Other lab data including local lab							Y
Vital Sign Analysis							
Vital Signs				Y			Y
Death Analysis							
Death							Y

NOTES:

- T = Table, F = Figure, L = Listing, Y = Yes display generated.
- Stats Analysis = Represents TFL related to any formal statistical analyses (i.e. modelling) conducted.
- Summary = Represents TFL related to any summaries (i.e. descriptive statistics) of the observed raw data.
- Individual = Represents FL related to any displays of individual subject observed raw data.

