8.3. Acceptability of CAB LA

The secondary acceptability analyses will be based on safety population, unless otherwise specified. All summary data and statistics are calculated from available data, unless otherwise specified.

To assess acceptability of the CAB LA, the proportion (with 95% confidence interval) of participants who would consider using CAB LA for HIV prevention in the future will be calculated among all subjects in the safety population (including those who terminated product use during the trial). Participants will be asked if they would consider using CAB LA for HIV prevention in the future at their Week 41 visit or at their withdrawal visit, whichever occurs first. Patients who are lost to follow up or with missing responses will be presented as such in a separate category.

Table 14 provides an overview of the planned acceptability analyses, with further details of data displays being presented in Appendix 14: List of Data Displays.

Table 14 Overview of Planned Acceptability Analyses

Display Type	Data Displays Generated						
	Stats Analysis			Summary		Individual	
	T	F	L	T	F	F	L
Acceptability of the CAB LA							
participants who would consider using CAB LA				Y			Y

NOTES:

- T = Table, F = Figure, L = Listing, Y = Yes display generated.
- Stats Analysis = Represents TFL related to any formal statistical analyses (i.e. modelling) conducted.
- Summary = Represents TFL related to any summaries (i.e. descriptive statistics) of the observed raw data.
- Individual = Represents FL related to any displays of individual subject observed raw data.

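### The SAP gives men who stop in the oral phase two end dates, so an on-treatment adverse event can belong to no phase; the exit assessment the protocol asks for is also missing from the schedule (minor)

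*Protocol*

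**What the plan says.** **Stopping in the oral phase.** Protocol 8.1: "Participants who discontinue study treatment during the oral phase will be withdrawn from the study". Protocol 8.2.1: "Participants that are discontinued from treatment during the Oral Phase will end their participation at that time". These men do not enter the follow-up phase, which is for men who have had at least one injection.

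**Exit assessment.** Protocol 8.2.1 adds: "Every effort should be made to complete the early termination study procedures and observations if the participant does not enter post-treatment follow-up". Protocol 8.2.2 directs the reader elsewhere for the content: "Refer to the SoA for data to be collected at the time of study discontinuation and follow-up". Protocol 10.3.2 and SAP 8.3 take the acceptability answer "at their Week 41 visit or at their withdrawal visit, whichever occurs first", and SAP 8.3 reports a proportion that "will be calculated among all subjects in the safety population (including those who terminated product use during the trial").

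**Schedule of Activities.** The columns are Screening, Day 1, Day 28, the visits from Week 5 to Week 41, Weeks 53, 65 and 77, and Week 89. No column, row or footnote describes early termination or withdrawal. Week 89 is the final visit and is tied to 56 weeks after the last injection. The visit footnote reads "Visit may occur in a window ± 3 Days".

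**Oral end date in the SAP.** For men who withdraw during the oral phase, SAP 8.2 analyses data "from the first date of taking oral CAB tablet up to the date of last study visit". SAP 10.4.1 ends the oral phase on the same date for anyone who stops before an injection. SAP 10.4.2.1, which assigns treatment states to adverse events, instead runs the on-oral state to seven days after withdrawal. The injection phase, the follow-up phase and the post-treatment state all need an injection date. Both SAP versions in the file carry these definitions.

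**Use of the phase.** SAP 7.1.2 tabulates adverse events by study phase and divides by the safety-population subjects who entered that phase.

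**The concern.** Oral safety is a secondary objective, and Protocol 10.3.1.1.2 promises a separate summary of events that are treatment emergent during oral dosing. For a man who is never injected, the SAP has two answers to when that period ends. An event between the two dates is on-treatment by state, but no phase can hold it: the oral phase has closed and the later phases cannot be evaluated. In a by-phase table he would then count in the denominator without his event in the numerator.

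The missing exit visit is a separate problem with the data themselves. The protocol asks for early termination procedures and points to the schedule, and the schedule does not list them. Each site would then choose what to do for a man who stops early. The lead-in exists to test individual tolerance before a long-acting injection, so men who stop during it are informative.

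**Working it through.** The plan states no figure for this point. The check applies the two SAP date rules to a man who is never injected, then reads the schedule for what he is due.

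**Rules.** Let L be the day of the last study visit and W the day of withdrawal.

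- Oral phase (SAP 8.2, 10.4.1): Day 1 to L.
- On-oral state (SAP 10.4.2.1): Day 1 to W + 7.
- Days on-treatment but in no phase: W + 7 − L, if positive.
- Days in the oral phase but not on-treatment: L − (W + 7), if positive.

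| L | W | W + 7 | Mismatch |
|---|---|---|---|
| 14 | 14 | 21 | Days 15–21: 7 days, no phase |
| 28 | 28 | 35 | Days 29–35: 7 days, no phase |
| 28 | 35 | 42 | Days 29–42: 14 days, no phase |
| 1 | 14 | 21 | Days 2–21: 20 days, no phase |
| 28 | 21 | 28 | none |
| 28 | 20 | 27 | Day 28: in phase, not on-treatment (reversed) |

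These are days on which the rules disagree, not lost events. The mismatch does not need a stop before Day 28: a man who attends Day 28 and is then not injected can also be affected. An event after both L and W + 7 has neither a phase nor a state.

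**Men concerned.** Protocol 5.2 plans about 48 men in the oral phase and about 40 in the injection phase: 48 − 40 = 8, and 8/48 = 16.7%.

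**Scheduled assessments for an early stop.** After Day 1, Day 28 is the only oral-phase visit in Table 1. With the three-day window it opens on Day 28 − 3 = Day 25. A stop on Days 1 to 24 precedes it, which is 24/28 = 85.7% of the dosing days (a share of days, not of men). After Day 1, the next adverse event review and the next hematology/chemistry are at Day 28, so a man who leaves earlier has neither scheduled.

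**If a site does hold an exit visit.** SAP 10.5.3 leaves unscheduled visits out of summary tables. SAP 7.1.3 uses them for maximum laboratory grade but not in the by-visit summary. SAP 10.3.1 relies on the visit name in the CRF, so how the exit visit is handled depends on an eCRF that is not among the documents.

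**Rash.** For a Grade 3 or 4 rash, Appendix 8 stops the drug but keeps the participant in the study under the Section 2 schedule. Protocol 8.1 withdraws anyone who stops in the oral phase. For an oral-phase rash both cannot be followed.

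**After the fix.** With a single end date, the later of L (visit or contact) and W + 7, phase and state end together and every mismatch in the table becomes zero.

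**The case against.** The strongest reply is that the gap is hard to reach. It needs an event that is recorded but starts after the last visit. Participation ends at the stop, Protocol 9.2.1 ties collection to scheduled time points, and sites need not seek events in former participants. An event that causes the stop precedes it. If a man returns for any further visit, that visit may itself become his last one and extend the phase. This stands, and it is why the impact is minor.

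Second, the AE-specific rule in SAP 10.4.2.1 might be the one programmed for the AE tables, in which case nothing would be missed. That is possible. But SAP 7.1.2 says study phase and SAP 8.2 uses the last-visit date, so the text does not settle it. The supportable statement is that an event can be missing, not that it will be.

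Third, the study reference manual or the eCRF may define the exit visit. Neither is available, and Protocol 8.2.2 points to the schedule. That section concerns withdrawal of consent and names data rather than a visit, so it supports the point only in part. For acceptability, SAP 8.3 already shows missing answers as a separate category.

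A reader might infer more than the documents support:

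- *That the error can only lower oral-phase incidence.* The last row of the table shows the reverse: a last visit more than seven days after withdrawal puts an event in the oral phase that is not on-treatment by state.
- *That early stoppers are singled out for missing vital signs.* The schedule has no vital signs at Day 28 for anyone; the next are at Week 5.
- *That only events known at the stop are followed.* Protocol 9.4.7 requires repeat testing of clinically significant abnormal values arising up to 14 days after the last oral dose. It schedules no test in that period, but it is not limited to known events.

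**Conclusion.** Both parts hold on the text, and the impact is minor. The SAP gives men who are never injected two oral end dates, so an event it calls on-treatment can be absent from a by-phase table while the man stays in the denominator. It remains in Listing 16. The protocol also calls for an exit assessment that its schedule does not list.

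The size in events cannot be determined: the documents give no event rate and no withdrawal timing, and few events are likely. The 8 of 48 men is a planning difference. A reader might take it as a maximum, but both planned numbers are approximate, replacements are allowed, and some of these men may complete Day 28. The day counts assume the withdrawal dates and last visits shown in the table. The study is single-arm and descriptive with no formal hypothesis, so no test is affected.

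**What to change.** 1. **SAP 8.2, 10.4.1 and 10.4.2.1.** For men who are never injected, use one oral end date: the later of the last study visit or contact and seven days after withdrawal. This covers both directions of the mismatch.
2. **Protocol Section 2.** Add an oral-phase early-withdrawal column with AE/SAE review and hematology/chemistry, and treat it in the SAP as a nominal visit so that its results enter the summaries. A brief adverse event contact about seven days later is optional. Word 8.1 and 8.2.1 so that participation ends after this visit, or after the contact if one is made.
3. **Appendix 8.** State which rule applies when a rash stops oral dosing, so that it agrees with 8.1.

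The cost is one date rule in three SAP sections, a short protocol amendment, and one exit visit for each man who stops in the oral phase: about 8 on the planned numbers, plus any replacements who also stop. If a man declines the visit or contact, the seven-day part of the rule still classifies any event that is reported.
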